Response (2)	Development of skin infection requiring topical or systemic antibiotic treatment by Week 16	Proportion reporting at least one infection on or before the Week 16 visit.

¹ Evaluated daily from Day 2 to 112.

² Sustained EASI-50 is a response which is seen at least 2 consecutive visits.

³ Sustained PP-NRS or SD-NRS improvement is defined as the relevant improvement shown at all evaluable days within at least a 14-day period.

The primary and selected secondary response endpoints relating to EASI, IGA and PP-NRS endpoints will be used in exploratory estimands which compare those who received topical corticosteroid rescue medication within specific windows with those who used no topical corticosteroid rescue therapy. These estimands will use all data as collected with no imputation for intercurrent events.

For Cohort 4 only, the primary and secondary endpoints relating to EASI, IGA, IGA*BSA and PP-NRS (those endpoints flagged in Table 11-3 for the use of secondary supplementary estimands) will also be used for exploratory estimands which compare the Cohort 1 EDP1815 treatment group with the Cohort 4 EDP1815 treatment group.

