7.1.2.1 Efficacy Data Point Set 1 (EDPS1)

EDPS1 consists of all data collected at a scheduled timepoint that is at least 28 days after use of TCS/TCI rescue therapy* or type 1 prohibited medication and before use of type 2 prohibited medication. Data collected less than 28 days after such use or data missing due to withdrawal from the study for reasons considered related to study medication** or data collected after use of type 2 prohibited medications will be replaced as follows:

- Continuous endpoints: value will be imputed with the last off-rescue¹ observation in the period before the event plus early termination visit in case of early study discontinuation (off-rescue is defined as data collected at least 28 days after use of rescue medication or type 1 prohibited medication)
- Responder endpoints: value will be imputed as non-response.
- Count endpoints: N/A (no count endpoint will use this DPS).

Data missing for other reasons, including early withdrawal from the study due to reasons not considered related to study medication will not be replaced and will be considered as missing.

Example 1: if patient completed 16 weeks of study with rescue therapy during week 3 and then during week 10 then responder endpoints will be analysed as shown in table:

Week 0	Week 2	Week 4	Week 8	Week 12	Week 16
As collected	As collected	Imputed as non-responder because there was a rescue therapy within 28 days before Week 4 visit	As collected	Imputed as non-responder because there was a rescue therapy within 28 days before Week 12 visit	As collected

Example 2: if patient completed 16 weeks of study with rescue therapy from Day 25 to Day 31 then responder endpoints will be analysed as shown in table:

Week 0	Week 2	Week 4	Week 8	Week 12	Week 16
As collected	As collected	Imputed as non-responder because there was a rescue therapy within 28 days before Week 4 visit	Imputed as non-responder because there was a rescue therapy within 28 days before Week 4 visit	As collected	As collected

Example 3: if patient withdrew study early due to the lack of efficacy after 12 weeks of treatment with rescue therapy during week 3 (unscheduled rescue therapy visit was not done) and then during week 10 (unscheduled rescue therapy visit was done at Week 9 prior to the rescue therapy start) then continuous endpoints will be analysed as shown in table:

Week 0	Week 2	Week 4	Week 8	Week 12	Week 16

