- Cohort 3 Placebo
- Cohort 3 EDP1815
- Cohort 4 Placebo (final analysis only)
- Cohort 4 EDP1815 (final analysis only)
- All Placebo
- All EDP1815
- Total

For cohorts 1-3 efficacy outputs, columns will be ordered and labelled as follows:

- All Placebo
- Cohort 1 EDP1815
- Cohort 2 EDP1815
- Cohort 3 EDP1815
- Cohorts 2+3 EDP1815
- All EDP1815

For cohort 4 efficacy outputs, columns will be ordered and labelled as follows:

- Cohort 4 Placebo
- Cohort 4 Matched Placebo
- Cohort 4 EDP1815
- Cohort 1 EDP1815

For concomitant medication and safety outputs, columns will be ordered and labelled as follows:

- All Placebo
- Cohort 1 EDP1815
- Cohort 2 EDP1815
- Cohort 3 EDP1815
- Cohort 4 EDP1815 (final analysis only)
- All EDP1815

For the analysis:

- For study disposition summaries where it is appropriate to report information on participants who failed screening, the enrolled population will be used.
- For safety summaries, where data is assigned to specific scheduled visits, the safety population with SDPS1 will be used.
- For safety summaries, where all other safety data is presented (including adverse events and worst-case change from baseline endpoints), the safety population with SDPS2 will be used.
- For the primary estimand and all secondary and exploratory estimands, full analysis population with EDPS1 will be used.
- For the supplementary estimands for the primary endpoint, full analysis population with EDPS2-EDPS5 will be used.
- Selected secondary response endpoints will also have secondary supplementary estimands: full analysis population with EDPS2 and EDPS6 will be used for endpoints based on EASI, vIGA and PP-NRS.
- For the secondary count endpoints, full analysis population with EDPS7 will be used.
- For the exploratory endpoints, full analysis population with EDPS1 will be used.
- For all other summaries and analyses the full analysis population will be used.

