9.5.1 Exploratory Efficacy Endpoints

The exploratory endpoints will be summarised using statistics appropriate to the endpoint as described below.

Continuous, time to event and response exploratory endpoints estimands will use the same intercurrent event strategy as the primary estimand (EDPS1 will be used). Where intercurrent event strategy is composite, for continuous endpoints value will be imputed with the last off-rescue observation.

Last off-rescue observation is defined as the last off-rescue observation in the period before the corresponding intercurrent event plus early termination visit in case of early study discontinuation (off-rescue is defined as data collected at least 28 days after use of rescue medication or type 1 prohibited medication).

Count exploratory endpoints and response subgroup endpoints will use EDPS7 (estimand includes all data as collected prior to completion or withdrawal from the study).

Exploratory estimands will be evaluated at all timepoints at which the relevant endpoints are collected.

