9.5.1.5 Count Exploratory Endpoints

Response exploratory endpoints:

- Number of uses of topical antimicrobial or systemic antibiotic treatment for skin infections by Week 16.

The population summary measure of interest will be the proportion of participants reporting at least one infection on or before the Week 16 visit in each treatment group.

The number and proportion of participants with skin infection requiring topical or systemic antibiotic treatment at least once during the study will be presented. Histogram of the number of courses will be plotted.

10 Safety Analyses

The Safety population will be used for all summaries of Safety. All safety endpoints will be listed.

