The datasets for the cohorts 1-3 and final analyses will follow analysis dataset model (ADaM) data specifications and will use standard data tabulation model (SDTM) data sets provided by [REDACTED] data management as the source data.

All analyses will be performed using SAS version 9.4 or higher (SAS Institute, Cary, NC, USA).

13 Summary of Changes from the Protocol

The SAP is based on the latest Protocol v5.0.

Table 44: Summary of Changes from the Protocol

Protocol Version	Summary of Change	Justification for change
V5.0	"Percentage of Participants developing skin infections requiring topical or systemic antibiotic treatment [Time Frame: Week 16]" endpoint changed to "Percentage of participants requiring topical antimicrobial or systemic antibiotic treatment for skin infections by Week 16"	Antimicrobials may be prescribed in order to prevent possible skin infections and these cases also needs to be considered
V5.0	Rescue therapy endpoints defined in the Protocol will only consider TCS/TCI rescue therapy	TCS/TCI rescue therapy is of interest. Exploratory endpoint to assess antimicrobial therapy modified to cover all antimicrobial rescue therapy
V5.0	Emollient compliance will be calculated through only Treatment Period (from Day 1 till the last dose of IMP) and not Follow-up. Previously the whole study period was considered.	Only compliance during treatment period is of interest and may affect efficacy
V5.0	Intercurrent event of TCS rescue therapy use will also include TCI rescue therapy	TCS/TCI rescue therapy is of interest.
V5.0	Prohibited medications intercurrent events (previously treated as Protocol Deviations events) are separated to type 1 and type 2. Type 1 prohibited medications are considered equivalent to TCS/TCI rescue therapy intercurrent event. Type 2 prohibited medications are considered equivalent to study withdrawal due to treatment related reason from the time of start of medication.	Prohibited medications have potential to affect efficacy and appropriate intercurrent event strategies should be used
V5.0	Other Protocol Deviations affecting efficacy added as possible intercurrent events	Not all Protocol Deviations affecting efficacy were listed initially
V5.0	Interim analysis goal changed from being a sample size recalculation to just checking for the balance between the treatment groups.	Evelo decided to not increase sample size.

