14.2.39	Summary of Time to First Achievement of PP-NRS Score with a ≥ 2 Point Sustained Improvement from Baseline for Participants with a Score of ≥ 2 at Baseline	FAS	EDPS1	
14.2.40	Summary of Time to First Achievement of PP-NRS Score with a ≥ 4 Point Improvement from Baseline for Participants with a Score of ≥ 4 at Baseline	FAS	EDPS1	
14.2.41	Summary of Time to First Achievement of PP-NRS Score with a ≥ 4 Point Sustained Improvement from Baseline for Participants with a Score of ≥ 4 at Baseline	FAS	EDPS1	
14.2.42	Summary of Time to First Achievement of SD-NRS Score with a ≥ 2 Point Improvement from Baseline for Participants with a Score of ≥ 2 at Baseline	FAS	EDPS1	
14.2.43	Summary of Time to First Achievement of SD-NRS Score with a ≥ 2 Point Sustained Improvement from Baseline for Participants with a Score of ≥ 2 at Baseline	FAS	EDPS1	
14.2.44	Summary of vIGA of 0 or 1 With a ≥ 2 Point Improvement from Screening Response	FAS	EDPS1	
14.2.45	Summary of Percentage Change from Screening in EASI Score	FAS	EDPS1	
14.2.46	Summary of Absolute Change from Screening in EASI Score	FAS	EDPS1	
14.2.47	Summary of Topical Antimicrobial or Systemic Antibiotic Rescue Therapy Use on or before Week 16	FAS	EDPS1	
14.2.48	Summary of Absolute Change from Baseline in SF-12 MCS	FAS	EDPS1	
14.2.49	Summary of Absolute Change from Baseline in SF-12 PCS	FAS	EDPS1	
14.2.50	Summary of Absolute Change from Baseline in HADS Anxiety Score	FAS	EDPS1	
14.2.51	Summary of Absolute Change from Baseline in HADS Depression Score	FAS	EDPS1	

Number	Title	Population	Data Point Set	Programming notes
14.2.52	Summary of Absolute Change from Baseline in ADCT Score	FAS	EDPS1	

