14.2.41	Kaplan-Meier Survival Curve for Time to First Achievement of PP-NRS Score with a ≥ 4 Point Sustained Improvement from Baseline for Participants with a Score of ≥ 4 at Baseline	FAS	EDPS1	
14.2.42	Kaplan-Meier Survival Curve for Time to First Achievement of SD-NRS Score with a ≥ 2 Point Improvement from Baseline for Participants with a Score of ≥ 2 at Baseline	FAS	EDPS1	
14.2.43	Kaplan-Meier Survival Curve for Time to First Achievement of SD-NRS Score with a ≥ 2 Point Sustained Improvement from Baseline for Participants with a Score of ≥ 2 at Baseline	FAS	EDPS1	
14.2.44	Proportion (95% CI) of Participants Achieving vIGA of 0 or 1 With a ≥ 2 Point Improvement from Screening Response	FAS	EDPS1	
14.2.45.1	Waterfall Plot of Percentage Change from Screening in EASI Score at Week 16	FAS	EDPS1	
14.2.45.2	Mean (SD) Percentage Change from Screening in EASI Score	FAS	EDPS1	

Statistical Analysis Plan
Version 2.0, Final 16-Jan-2023

EDP1815-207

Number	Title	Population	Data Point Set	Programming notes
14.2.46.1	Waterfall Plot of Absolute Change from Screening in EASI Score at Week 16	FAS	EDPS1	
14.2.46.2	Mean (SD) Absolute Change from Screening in EASI Score	FAS	EDPS1	
14.2.47	Histogram of Number of Courses of Topical Antimicrobial or Systemic Antibiotic Rescue Therapy on or before Week 16	FAS	EDPS1	
14.2.48.1	Waterfall Plot of Absolute Change from Baseline in SF-12 MCS at Week 16	FAS	EDPS1	
14.2.48.2	Mean (SD) Absolute Change from Baseline in SF-12 MCS	FAS	EDPS1	
14.2.49.1	Waterfall Plot of Absolute Change from Baseline in SF-12 PCS at Week 16	FAS	EDPS1	
14.2.49.2	Mean (SD) Absolute Change from Baseline in SF-12 PCS	FAS	EDPS1	
14.2.50.1	Waterfall Plot of Absolute Change from Baseline in HADS Anxiety Score at Week 16	FAS	EDPS1	
14.2.50.2	Mean (SD) Absolute Change from Baseline in HADS Anxiety Score	FAS	EDPS1	
14.2.51.1	Waterfall Plot of Absolute Change from Baseline in HADS Depression Score at Week 16	FAS	EDPS1	
14.2.51.2	Mean (SD) Absolute Change from Baseline in HADS Depression Score	FAS	EDPS1	
14.2.52.1	Waterfall Plot of Absolute Change from Baseline in ADCT Score at Week 16	FAS	EDPS1	
14.2.52.2	Mean (SD) Absolute Change from Baseline in ADCT Score	FAS	EDPS1	
14.2.56	Mean Absolute Change from Baseline in PP-NRS Score - Daily	FAS	EDPS1	
14.2.57	Proportion of Participants Achieving PP-NRS Score with a ≥ 2 Point Improvement from Baseline for Participants with a Score of ≥ 2 at Baseline - Daily	FAS	EDPS1	

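### The SAP assigns the antimicrobial/skin-infection endpoint to two different data point sets, and EDPS1, the one in the output list, has no usable rule for it

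*SAP*

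**What the plan says.** **Definition.** Protocol section 11.3.3 (Table 11-3) lists "Development of skin infection requiring topical or systemic antibiotic treatment by Week 16" as a response endpoint and places exploratory estimands on the FAS with EDPS1. Protocol section 11.1.2 exempts count endpoints from EDPS1. SAP section 13 widens the endpoint to antimicrobial treatment, with the reason: "Antimicrobials may be prescribed in order to prevent possible skin infections and these cases also needs to be considered". SAP section 4.2 words the result as a percentage of participants. SAP section 9.5.1.5 words it as a number of uses, under a count heading but with a lead-in that calls it a response endpoint, and makes the summary measure the "proportion of participants reporting at least one infection on or before the Week 16 visit in each treatment group".

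**Data point set.** The output list gives EDPS1 for Table 14.2.47, "Summary of Topical Antimicrobial or Systemic Antibiotic Rescue Therapy Use on or before Week 16", and for Figure 14.2.47, "Histogram of Number of Courses of Topical Antimicrobial or Systemic Antibiotic Rescue Therapy on or before Week 16". SAP section 8 has the general rule: "For the exploratory endpoints, full analysis population with EDPS1 will be used". SAP section 9.5.1 says otherwise: "Count exploratory endpoints and response subgroup endpoints will use EDPS7".

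**EDPS1 itself.** SAP section 7.1.2.1 has three triggers for replacing data: less than 28 days since TCS/TCI rescue or type 1 prohibited medication; any use of type 2 prohibited medication beforehand; and data missing because of a treatment-related withdrawal. For binary endpoints the rule is: "Responder endpoints: value will be imputed as non-response". For counts it gives no rule and says that none will use this set.

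**The concern.** A programmer working from the output list and one working from section 9.5.1 would build this table on different data. The histogram is worse placed: it plots a number of courses on a set that has no rule for counts.

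Direction matters too. EDPS1 was designed for outcomes such as EASI-50, where scoring a participant as a non-responder is the unfavourable value. Here the event being counted is itself unfavourable, so the same imputation becomes the favourable value. Protocol section 6.9.1.2 links uncontrolled disease to secondary skin infection, so the participants who trigger EDPS1 may well be those more likely to have the event. If rescue use differs by arm, any loss of events would differ by arm as well.

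There is also a labelling problem. The endpoint now includes antimicrobials given preventively, but section 9.5.1.5 still describes the result as participants with an infection.

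**Working it through.** No planned figure is at issue, so the check is a comparison of the text, followed by an illustration of scale.

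**1. Which set applies?**

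| Points to EDPS1 | Points to EDPS7 |
|---|---|
| SAP 15.2.1, Table 14.2.47 | SAP 9.5.1, rule for exploratory counts |
| SAP 15.2.2, Figure 14.2.47 | SAP 9.5.1.5, endpoint placed under counts |
| SAP 8, general exploratory rule | SAP 7.1.2.1, counts barred from EDPS1 |
| Protocol 11.3.3, classed as a response | Protocol 11.1.2, counts exempt from EDPS1 |

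The comparable TCS/TCI rescue outputs, Tables 14.2.32 to 14.2.34, are on EDPS7, including 14.2.34, which is a proportion. So is Listing 16.2.6.11, which holds these same antimicrobial records. The exploratory tables of response by rescue use (14.2.1.5 and similar) are also on EDPS7, so the output list already departs from the general rule in section 8. EDPS7 is the consistent choice.

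**2. What would a literal EDPS1 do?** Assume the endpoint is programmed as a Week 16 responder value, with non-response coded as no use. A participant with a recorded antimicrobial course would be set to no event in two cases: TCS/TCI rescue or type 1 medication less than 28 days before Week 16, or type 2 medication at any earlier point. An antimicrobial alone, or rescue 28 days or more before Week 16, triggers nothing.

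**3. How large could it be?** The documents give neither infection nor rescue rates. Let f be the share of participants with an EDPS1 trigger at Week 16, q the event proportion in the others, and RR the risk ratio in triggered versus other participants.

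- True proportion = (1 − f)q + f·q·RR
- Reported proportion = (1 − f)q
- Share of participants with an event who are lost = f·RR / [(1 − f) + f·RR], which does not depend on q

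Assumed ranges are f from 10% to 30% and RR from 1 to 3.

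- Low end: 0.1 × 1 / (0.9 + 0.1) = 10%
- High end: 0.3 × 3 / (0.7 + 0.9) = 0.9/1.6 = 56%
- Example with q = 10%, f = 20%, RR = 3: true 0.08 + 0.06 = 14.0%, reported 8.0%. In a planned group of 75 that is 10.5 against 6.0 participants.
- Unequal triggers with q = 10%, RR = 3, and f = 30% in one arm and 10% in the other: true 16.0% against 12.0%, reported 7.0% against 9.0%. This pair was chosen to show that the order can reverse; it is not a forecast.

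Under EDPS7 nothing is imputed and the loss is zero.

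**The case against.** The strongest reply is that this is a labelling slip that the SAP body already corrects: sections 9.5.1 and 9.5.1.5 send the endpoint to EDPS7, and EDPS1 refuses counts. EDPS1 is also written for data collected at scheduled timepoints, whereas SAP section 5.3.3.14 records rescue by course as concomitant medication. Nothing says how EDPS1 would act on a cumulative event, or what non-response means for an unfavourable one. The events also stay visible in Listing 16.2.6.11, in the concomitant-medication summaries and in the adverse-event tables, none of which uses this imputation.

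Most of that stands, and it limits the point. It does not show which instruction prevails, because the output list, section 8 and the protocol all say EDPS1.

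A reader might infer more: that infections in recently rescued participants and in treatment-related withdrawals will be erased, with certainty for a steroid-antibiotic combination. The documents do not support this.

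- The EDPS7 instruction may be the one followed, in which case nothing is lost.
- For related withdrawal, EDPS1 replaces only missing data, and SAP section 9.3.1 keeps data that were collected. For unrelated withdrawal nothing is replaced. An infection recorded before withdrawal is observed data and is lost only if the endpoint is first recast as a Week 16 visit value.
- The combination product in Protocol section 6.9.1.2 is both an antimicrobial and a topical steroid. SAP section 7.1.2 leaves classification to a sponsor clinician and does not say how a combination is labelled, so the outcome is possible but not certain.

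**Conclusion.** The contradiction is firm: the SAP gives two data point sets for one endpoint, and the one in the output list has no valid rule for it. The mismatch between the widened antimicrobial-use definition and the infection wording in section 9.5.1.5 is also firm, although the table title already speaks of use.

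The loss of events is conditional. It needs EDPS1 to prevail, its responder rule to be applied to a Week 16 value, and non-response to be read as no event. The range of 10% to 56% rests wholly on assumed inputs and shows only that the loss need not be negligible if those conditions hold.

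The point is minor. The endpoint is exploratory and summarised without inference, and no primary or secondary result changes.

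**What to change.** - Relabel Table 14.2.47 and Figure 14.2.47 as EDPS7, in line with Tables 14.2.32 to 14.2.34 and Listing 16.2.6.11.
- Add an exception for this endpoint to the exploratory rule in SAP section 8, and record it in SAP section 13 as a change from Protocol section 11.3.3.
- State in section 9.5.1.5 that every recorded use from Day 1 to Week 16, or to study withdrawal if earlier, counts as collected. Correct the lead-in, and say that the table gives the proportion with at least one use and the figure the number of courses.
- Replace the infection wording in section 9.5.1.5 with antimicrobial use, to match the definition in section 13. A separate row for treated infections, based on the indication recorded under Protocol section 6.9, is optional.

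The cost is two output-list entries and a few lines of SAP text. No new data are needed and no clinical procedure changes. The only price is one stated departure from the common EDPS1 rule.

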15.2.2 Figures

Number	Title	Population	Data Point Set	Programming notes
14.2.1.2.1	Actual and Predicted Probability (95% CI) of EASI-50 Response At Week 16	FAS	EDPS1	Include in TLR
14.2.1.2.2	Actual and Predicted Probability (95% CI) of EASI-50 Response At Week 16	FAS	EDPS2	
14.2.1.2.3	Actual and Predicted Probability (95% CI) of EASI-50 Response At Week 16	FAS	EDPS3	
14.2.1.2.4	Actual and Predicted Probability (95% CI) of EASI-50 Response At Week 16	FAS	EDPS4	
14.2.1.2.5	Actual and Predicted Probability (95% CI) of EASI-50 Response At Week 16	FAS	EDPS5	
14.2.1.2.6	Actual and Predicted Probability (95% CI) of EASI-50 Response At Week 16	FAS	EDPS6	Include in TLR
14.2.1.3.1	Adjusted Odds Ratio (95% CI) for Achievement of EASI-50 Over Time - GLMM	FAS	EDPS1	Include in TLR
14.2.1.3.2	Adjusted Odds Ratio (95% CI) for Achievement of EASI-50 Over Time - GLMM	FAS	EDPS2	
14.2.1.3.3	Adjusted Odds Ratio (95% CI) for Achievement of EASI-50 Over Time - GLMM	FAS	EDPS6	Include in TLR
14.2.2.1.1	Proportion (95% CI) of Participants Achieving EASI-75 At Week 16	FAS	EDPS1	Include in TLR
14.2.2.1.3	Proportion (95% CI) of Participants Achieving EASI-75 At Week 16	FAS	EDPS6	
14.2.2.2.1	Adjusted Odds Ratio (95% CI) for Achievement of EASI-75 Over Time - GLMM	FAS	EDPS1	

Statistical Analysis Plan
Version 2.0, Final 16-Jan-2023

EDP1815-207

Number	Title	Population	Data Point Set	Programming notes
14.2.2.2.3	Adjusted Odds Ratio (95% CI) for Achievement of EASI-75 Over Time - GLMM	FAS	EDPS6	
14.2.3.1.1	Proportion (95% CI) of Participants Achieving EASI-90 At Week 16	FAS	EDPS1	Include in TLR
14.2.3.1.3	Proportion (95% CI) of Participants Achieving EASI-90 At Week 16	FAS	EDPS6	
14.2.3.2.1	Adjusted Odds Ratio (95% CI) for Achievement of EASI-90 Over Time - GLMM	FAS	EDPS1	
14.2.3.2.3	Adjusted Odds Ratio (95% CI) for Achievement of EASI-90 Over Time - GLMM	FAS	EDPS6	
14.2.4.1.1	Waterfall Plot of Percentage Change from Baseline in EASI Score at Week 16	FAS	EDPS1	Include in TLR
14.2.4.1.2	Waterfall plot of Percentage Change from Baseline in EASI Score at Weeks 4, 8 12 and 16 with Week 16 EASI-50 Responders Highlighted	FAS	EDPS1	
14.2.4.1.3	Waterfall plot of Percentage Change from Baseline in EASI Score at Weeks 4, 8 12 and 16 with Week 16 EASI-75 Responders Highlighted	FAS	EDPS1	
14.2.4.2.1	LS Mean (95% CI) Percentage Change in EASI Score Over Time - MMRM	FAS	EDPS1	
14.2.4.3.1	LS Mean Difference (95% CI) in Percentage Change from Baseline in EASI Score - MMRM	FAS	EDPS1	
14.2.5.1.1	Waterfall Plot of Absolute Change from Baseline in EASI Score at Week 16	FAS	EDPS1	
14.2.5.2.1	LS Mean (95% CI) Absolute Change in EASI Score Over Time – MMRM	FAS	EDPS1	
14.2.5.3.1	LS Mean Difference (95% CI) in Absolute Change from Baseline in EASI Score - MMRM	FAS	EDPS1	
14.2.7.1.1	Proportion (95% CI) of Participants Achieving vIGA of 0 or 1 With a ≥ 2 Point Improvement from Baseline Response	FAS	EDPS1	Include in TLR
14.2.7.1.3	Proportion (95% CI) of Participants Achieving vIGA of 0 or 1 With a ≥ 2 Point Improvement from Baseline Response	FAS	EDPS6	

Statistical Analysis Plan
Version 2.0, Final 16-Jan-2023

EDP1815-207

Number	Title	Population	Data Point Set	Programming notes
14.2.7.2.1	Adjusted Odds Ratio (95% CI) for Achievement of vIGA of 0 or 1 With a ≥ 2 Point Improvement from Baseline Response - GLMM	FAS	EDPS1	
14.2.7.2.3	Adjusted Odds Ratio (95% CI) for Achievement of vIGA of 0 or 1 With a ≥ 2 Point Improvement from Baseline Response - GLMM	FAS	EDPS6	
14.2.8.1.1	Proportion (95% CI) of Participants Achieving vIGA of 0 or 1 Response	FAS	EDPS1	Include in TLR
14.2.8.1.3	Proportion (95% CI) of Participants Achieving vIGA of 0 or 1 Response	FAS	EDPS6	
14.2.8.2.1	Adjusted Odds Ratio (95% CI) for Achievement of vIGA of 0 or 1 Response - GLMM	FAS	EDPS1	
14.2.8.2.3	Adjusted Odds Ratio (95% CI) for Achievement of vIGA of 0 or 1 Response - GLMM	FAS	EDPS6	
14.2.9.1.1	Proportion (95% CI) of Participants Achieving vIGA of 0 Response at Week 16	FAS	EDPS1	
14.2.9.1.3	Proportion (95% CI) of Participants Achieving vIGA of 0 Response at Week 16	FAS	EDPS6	
14.2.9.2.1	Adjusted Odds Ratio (95% CI) for Achievement of vIGA of 0 Response - GLMM	FAS	EDPS1	
14.2.9.2.3	Adjusted Odds Ratio (95% CI) for Achievement of vIGA of 0 Response - GLMM	FAS	EDPS6	
14.2.10.1.1	Waterfall Plot of Percentage Change from Baseline in vIGA*BSA at Week 16	FAS	EDPS1	
14.2.10.2.1	LS Mean (95% CI) Percentage Change from Baseline in vIGA*BSA - MMRM	FAS	EDPS1	
14.2.10.3.1	LS Mean Difference (95% CI) in Percentage Change from Baseline in vIGA*BSA - MMRM	FAS	EDPS1	
14.2.12.1	Waterfall Plot of Percentage Change from Baseline in BSA at Week 16	FAS	EDPS1	
14.2.12.2	LS Mean (95% CI) Percentage Change from Baseline in BSA - MMRM	FAS	EDPS1	
14.2.12.3	LS Mean Difference (95% CI) in Percentage Change from Baseline in BSA - MMRM	FAS	EDPS1	

Statistical Analysis Plan
Version 2.0, Final 16-Jan-2023

EDP1815-207

Number	Title	Population	Data Point Set	Programming notes
14.2.13.1	Waterfall Plot of Absolute Change from Baseline in BSA at Week 16	FAS	EDPS1	
14.2.13.2	LS Mean (95% CI) Absolute Change from Baseline in BSA - MMRM	FAS	EDPS1	
14.2.13.3	LS Mean Difference (95% CI) in Absolute Change from Baseline in BSA - MMRM	FAS	EDPS1	
14.2.14.1	Proportion (95% CI) of Participants Achieving BSA-50 Response at Week 16	FAS	EDPS1	
14.2.14.2	Adjusted Odds Ratio (95% CI) for Achievement of BSA-50 Response - GLMM	FAS	EDPS1	
14.2.15.1	Proportion (95% CI) of Participants Achieving BSA-75 Response at Week 16	FAS	EDPS1	
14.2.15.2	Adjusted Odds Ratio (95% CI) for Achievement of BSA-75 Response – GLMM	FAS	EDPS1	
14.2.16.1	Proportion (95% CI) of Participants Achieving BSA Reduction to $\leq 3\%$ at Week 16	FAS	EDPS1	
14.2.16.2	Adjusted Odds Ratio (95% CI) for Achievement of BSA Reduction to $\leq 3\%$ - GLMM	FAS	EDPS1	
14.2.17.1	Waterfall Plot of Percentage Change from Baseline in SCORAD Score at Week 16	FAS	EDPS1	
14.2.17.2	LS Mean (95% CI) Percentage Change from Baseline in SCORAD Score - MMRM	FAS	EDPS1	
14.2.17.3	LS Mean Difference (95% CI) in Percentage Change from Baseline in SCORAD Score - MMRM	FAS	EDPS1	
14.2.18.1	Waterfall Plot of Absolute Change from Baseline in SCORAD Score at Week 16	FAS	EDPS1	
14.2.18.2	LS Mean (95% CI) Absolute Change from Baseline in SCORAD Score - MMRM	FAS	EDPS1	
14.2.18.3	LS Mean Difference (95% CI) in Absolute Change from Baseline in SCORAD Score - MMRM	FAS	EDPS1	

Number	Title	Population	Data Point Set	Programming notes
14.2.53.1	Proportion (95% CI) of Participants Achieving SCORAD-35 Response at Week 16	FAS	EDPS1	
14.2.53.2	Adjusted Odds Ratio (95% CI) for Achievement of SCORAD-35 Response - GLMM	FAS	EDPS1	
14.2.19.1	Proportion (95% CI) of Participants Achieving SCORAD-50 Response at Week 16	FAS	EDPS1	
14.2.19.2	Adjusted Odds Ratio (95% CI) for Achievement of SCORAD-50 Response - GLMM	FAS	EDPS1	
14.2.20.1	Proportion (95% CI) of Participants Achieving SCORAD-75 Response at Week 16	FAS	EDPS1	
14.2.20.2	Adjusted Odds Ratio (95% CI) for Achievement of SCORAD-75 Response – GLMM	FAS	EDPS1	
14.2.22.1	Waterfall Plot of Absolute Change from Baseline in DLQI Score at Week 16	FAS	EDPS1	
14.2.22.2	LS Mean (95% CI) Absolute Change from Baseline in DLQI Score	FAS	EDPS1	
14.2.22.3	LS Mean Difference (95% CI) in Absolute Change from Baseline in DLQI Score - MMRM	FAS	EDPS1	
14.2.23.1	Proportion (95% CI) of Participants Achieving DLQI With a ≥ 4 Point Improvement from Baseline for Participants with a Score of ≥ 4 at Baseline at Week 16	FAS	EDPS1	
14.2.23.2	Adjusted Odds Ratio (95% CI) for Achievement of DLQI With a ≥ 4 Point Improvement from Baseline for Participants with a Score of ≥ 4 at Baseline - GLMM	FAS	EDPS1	
14.2.24.1.1	Waterfall Plot of Absolute Change from Baseline in PP-NRS Score at Week 16	FAS	EDPS1	
14.2.24.2.1	LS Mean (95% CI) Absolute Change from Baseline in PP-NRS Score - MMRM	FAS	EDPS1	

Number	Title	Population	Data Point Set	Programming notes
14.2.24.3.1	LS Mean Difference (95% CI) in Absolute Change from Baseline in PP-NRS Score - MMRM	FAS	EDPS1	
14.2.25.1.1	Proportion (95% CI) of Participants Achieving PP-NRS With a ≥ 2 Point Improvement from Baseline for Participants with a Score of ≥ 2 at Baseline at Week 16	FAS	EDPS1	
14.2.25.1.3	Proportion (95% CI) of Participants Achieving PP-NRS With a ≥ 2 Point Improvement from Baseline for Participants with a Score of ≥ 2 at Baseline at Week 16	FAS	EDPS6	
14.2.25.2.1	Adjusted Odds Ratio (95% CI) for Achievement of PP-NRS With a ≥ 2 Point Improvement from Baseline for Participants with a Score of ≥ 2 at Baseline - GLMM	FAS	EDPS1	
14.2.25.2.3	Adjusted Odds Ratio (95% CI) for Achievement of PP-NRS With a ≥ 2 Point Improvement from Baseline for Participants with a Score of ≥ 2 at Baseline - GLMM	FAS	EDPS6	
14.2.26.1.1	Proportion (95% CI) of Participants Achieving PP-NRS With a ≥ 4 Point Improvement from Baseline for Participants with a Score of ≥ 4 at Baseline at Week 16	FAS	EDPS1	
14.2.26.1.3	Proportion (95% CI) of Participants Achieving PP-NRS With a ≥ 4 Point Improvement from Baseline for Participants with a Score of ≥ 4 at Baseline at Week 16	FAS	EDPS6	
14.2.26.2.1	Adjusted Odds Ratio (95% CI) for Achievement of PP-NRS With a ≥ 4 Point Improvement from Baseline for Participants with a Score of ≥ 4 at Baseline - GLMM	FAS	EDPS1	
14.2.26.2.3	Adjusted Odds Ratio (95% CI) for Achievement of PP-NRS With a ≥ 4 Point Improvement from Baseline for Participants with a Score of ≥ 4 at Baseline - GLMM	FAS	EDPS6	
14.2.27.1	Waterfall Plot of Absolute Change from Baseline in SD-NRS Score at Week 16	FAS	EDPS1	

Number	Title	Population	Data Point Set	Programming notes
14.2.27.2	LS Mean (95% CI) Absolute Change from Baseline in SD-NRS Score - MMRM	FAS	EDPS1	
14.2.27.3	LS Mean Difference (95% CI) in Absolute Change from Baseline in SD-NRS Score - MMRM	FAS	EDPS1	
14.2.28.1	Proportion (95% CI) of Participants Achieving SD-NRS With a ≥ 2 Point Improvement from Baseline for Participants with a Score of ≥ 2 at Baseline at Week 16	FAS	EDPS1	
14.2.28.2	Adjusted Odds Ratio (95% CI) for Achievement of SD-NRS With a ≥ 2 Point Improvement from Baseline for Participants with a Score of ≥ 2 at Baseline - GLMM	FAS	EDPS1	
14.2.30.1	Waterfall Plot of Absolute Change from Baseline in POEM Score at Week 16	FAS	EDPS1	
14.2.30.2	LS Mean (95% CI) Absolute Change from Baseline in POEM Score - MMRM	FAS	EDPS1	
14.2.30.3	LS Mean Difference (95% CI) in Absolute Change from Baseline in POEM Score - MMRM	FAS	EDPS1	
14.2.31.1	Proportion (95% CI) of Participants Achieving POEM With a ≥ 4 Point Improvement from Baseline for Participants with a Score of ≥ 4 at Baseline at Week 16	FAS	EDPS1	Include in TLR
14.2.31.2	Adjusted Odds Ratio (95% CI) for Achievement of POEM With a ≥ 4 Point Improvement from Baseline for Participants with a Score of ≥ 4 at Baseline GLMM	FAS	EDPS1	
14.2.32	Histogram of Number of Courses of Rescue Therapy	FAS	EDPS7	
14.2.34.1	Proportion (95% CI) of Participants Not Requiring for Rescue Therapy on or before Week 16	FAS	EDPS7	
14.2.34.2	Adjusted Odds Ratio (95% CI) for Not Requiring for Rescue Therapy - GLMM	FAS	EDPS7	
14.2.35	Cumulative Incidence (95% CI) of EASI-50	FAS	EDPS1	

Statistical Analysis Plan
Version 2.0, Final 16-Jan-2023

EDP1815-207

Number	Title	Population	Data Point Set	Programming notes
14.2.36	Cumulative Incidence (95% CI) of Sustained EASI-50	FAS	EDPS1	
14.2.54	Cumulative Incidence (95% CI) of EASI-75	FAS	EDPS1	
14.2.37	Cumulative Incidence (95% CI) of IGA of 0 or 1 with a ≥ 2 Point Improvement from Baseline	FAS	EDPS1	
14.2.55	Cumulative Incidence (95% CI) of IGA of 0 or 1	FAS	EDPS1	
14.2.38	Kaplan-Meier Survival Curve for Time to First Achievement of PP-NRS Score with a ≥ 2 Point Improvement from Baseline for Participants with a Score of ≥ 2 at Baseline	FAS	EDPS1	
14.2.39	Kaplan-Meier Survival Curve for Time to First Achievement of PP-NRS Score with a ≥ 2 Point Sustained Improvement from Baseline for Participants with a Score of ≥ 2 at Baseline	FAS	EDPS1	
14.2.40	Kaplan-Meier Survival Curve for Time to First Achievement of PP-NRS Score with a ≥ 4 Point Improvement from Baseline for Participants with a Score of ≥ 4 at Baseline	FAS	EDPS1	
14.2.41	Kaplan-Meier Survival Curve for Time to First Achievement of PP-NRS Score with a ≥ 4 Point Sustained Improvement from Baseline for Participants with a Score of ≥ 4 at Baseline	FAS	EDPS1	
14.2.42	Kaplan-Meier Survival Curve for Time to First Achievement of SD-NRS Score with a ≥ 2 Point Improvement from Baseline for Participants with a Score of ≥ 2 at Baseline	FAS	EDPS1	
14.2.43	Kaplan-Meier Survival Curve for Time to First Achievement of SD-NRS Score with a ≥ 2 Point Sustained Improvement from Baseline for Participants with a Score of ≥ 2 at Baseline	FAS	EDPS1	
14.2.44	Proportion (95% CI) of Participants Achieving vIGA of 0 or 1 With a ≥ 2 Point Improvement from Screening Response	FAS	EDPS1	
14.2.45.1	Waterfall Plot of Percentage Change from Screening in EASI Score at Week 16	FAS	EDPS1	
14.2.45.2	Mean (SD) Percentage Change from Screening in EASI Score	FAS	EDPS1	

Statistical Analysis Plan
Version 2.0, Final 16-Jan-2023

EDP1815-207

Number	Title	Population	Data Point Set	Programming notes
14.2.46.1	Waterfall Plot of Absolute Change from Screening in EASI Score at Week 16	FAS	EDPS1	
14.2.46.2	Mean (SD) Absolute Change from Screening in EASI Score	FAS	EDPS1	
14.2.47	Histogram of Number of Courses of Topical Antimicrobial or Systemic Antibiotic Rescue Therapy on or before Week 16	FAS	EDPS1	
14.2.48.1	Waterfall Plot of Absolute Change from Baseline in SF-12 MCS at Week 16	FAS	EDPS1	
14.2.48.2	Mean (SD) Absolute Change from Baseline in SF-12 MCS	FAS	EDPS1	
14.2.49.1	Waterfall Plot of Absolute Change from Baseline in SF-12 PCS at Week 16	FAS	EDPS1	
14.2.49.2	Mean (SD) Absolute Change from Baseline in SF-12 PCS	FAS	EDPS1	
14.2.50.1	Waterfall Plot of Absolute Change from Baseline in HADS Anxiety Score at Week 16	FAS	EDPS1	
14.2.50.2	Mean (SD) Absolute Change from Baseline in HADS Anxiety Score	FAS	EDPS1	
14.2.51.1	Waterfall Plot of Absolute Change from Baseline in HADS Depression Score at Week 16	FAS	EDPS1	
14.2.51.2	Mean (SD) Absolute Change from Baseline in HADS Depression Score	FAS	EDPS1	
14.2.52.1	Waterfall Plot of Absolute Change from Baseline in ADCT Score at Week 16	FAS	EDPS1	
14.2.52.2	Mean (SD) Absolute Change from Baseline in ADCT Score	FAS	EDPS1	
14.2.56	Mean Absolute Change from Baseline in PP-NRS Score - Daily	FAS	EDPS1	
14.2.57	Proportion of Participants Achieving PP-NRS Score with a ≥ 2 Point Improvement from Baseline for Participants with a Score of ≥ 2 at Baseline - Daily	FAS	EDPS1	
14.2.58	Proportion of Participants Achieving PP-NRS Score with a ≥ 4 Point Improvement from Baseline for Participants with a Score of ≥ 4 at Baseline - Daily	FAS	EDPS1	
14.2.59	Mean Absolute Change from Baseline in SD-NRS Score - Daily	FAS	EDPS1	

Number	Title	Population	Data Point Set	Programming notes
14.2.60	Proportion of Participants Achieving SD-NRS Score with a ≥ 2 Point Improvement from Baseline for Participants with a Score of ≥ 2 at Baseline - Daily	FAS	EDPS1	

